## **5.0 PROCEDURES**

**Screening** Individuals that are interested in participating in the study will be asked to complete a phone screen with a study team member. During the phone screen, the research staff will read a brief recruitment script and ask if the participant is interested in participating. If the individual is interested and willing, they are asked to complete a phone screen. The phone screen can be scheduled for immediately following the recruitment script or at a time convenient for the potential participant.

The phone screen will assess the following: basic demographic information, and self-identified T2D diagnosis. Individuals will be eligible for a baseline interview if they meet demographic criteria (self identified as African American/black, and over eighteen years old), and self-report having Type 2 Diabetes.

Upon completion of the phone screen, the study team member will inform the individual if they are eligible to complete the baseline interview. If the individual is eligible, a baseline assessment will be scheduled and details will be given to the individual. The purpose of this initial screen is to invite research candidates to additional eligibility screening (Baseline Assessment) having met initial criteria and for the research candidates to provide consent to answering questions at the in-person Baseline Assessment which involve Private Health Information, to be used for determining eligibility.

**Baseline Assessment** (Assessment Battery) All individuals that meet initial phone screening criteria and agree to participate will complete a baseline assessment. Baseline assessment will be held in person at Detroit Community Health Center (DCHC), by phone or virtually with a study team member. During the assessment the participant will be asked to complete the informed consent (with electronic signature using SignNow), questionnaires, interviews, and physiologic testing to determine if the participant is eligible to participate based on inclusion and exclusion criteria. Baseline assessments will last about sixty minutes. The PI will train all research staff in standardized data collection. Participants will be paid \$20 for completing the assessment and the same assessments at T0 (baseline) and T2 (treatment termination).

**Randomization** Participants will be randomized to the virtual empowerment based DSME/S or a control group using a 50/50 randomization scheme. Participants will be aware if they are in the intervention group or the control group.

**Intervention (virtual empowerment-based DSME/S n=30)** Participants randomized into the virtual empowerment-based DSME/S group will receive 10 hours of DSME/S delivered by a Certified Diabetes Care and Education Specialist (CDCES) over 8 weeks delivered via the Zoom for Health at U-M service may be used for Protected Health Information (PHI, regulated by HIPAA). To ensure treatment fidelity, three DSME/S sessions will be selected at random and recorded and rated for fidelity to the above content by our research team.

**Control Group (Control n=30)** Participants randomized to enhanced usual care will receive referrals to community mental health providers, pedometers, gym memberships to a community-based venue, and intervention patient manuals. Based on several years of experience in Detroit, providing all participants with referrals, pedometers, and educational materials minimizes ethical concerns regarding assignment of underserved populations to receive a no-treatment control.

**Follow-Ups** Follow up assessments for both the virtual empowerment-based DSME/S group and control group will occur at three months (post-treatment assessment). Participants will return to the DCHC for follow-up assessments, telephonically, or virtually and the same measurements and surveys will be completed. Participants will be compensated \$20 for completing each assessment. Data will be stored in REDCap, a secure, web-based application hosted at UM.

**Maintenance of Samples** Strategies will be used to encourage attendance of group sessions and to complete follow up interviews. Reminder emails, texts and/or calls

will be sent before each session to remind participants by the study team. In addition, the study team will collect participant contact information from baseline through the follow up phase. The study team will also ask participants to provide additional contact person(s) that the study team can contact if they cannot reach the participant.

**Participant Retention** The following procedures will be used to minimize participant attrition: 1) Data collection sessions will be completed at the DCHC site in order to maximize the convenience of data collection for subjects, and 2) multiple techniques are used to increase the likelihood that participants will keep their data collection appointments, including advanced scheduling, multiple reminder letters, and phone reminders. Participants who withdraw will still be asked to participate in study data.

**Data Collection & Data Safety** For Phase II (intervention), research data will be collected through the following methods: finger stick capillary blood samples, blood pressure measurements, weight, height, exit interviews regarding treatment satisfaction, surveys, audio recorded interviews and treatment sessions, and transcribed interviews and treatment session recordings. All data will be obtained specifically for research purposes and will be collected only with informed consent over the course of the award period.

At the time of study enrollment, participants will be assigned a study identification number to be used in all study materials and data for the duration of the study. All identifying information will be separated from the data and laboratory values. A master list that contains participants names and study identification number will be kept in a locked filing cabinet within a locked office in the School of Social Work at the University of Michigan. Audiotapes of interviews and treatment sessions will be stored securely on a password protected computer only accessible to study personnel and will be destroyed upon study completion. We will use DropBox, a secure platform to share these recordings, transcriptions, and other study data between study team members.

The principal investigator ([name]) and the research assistants will be the only persons who have access to the file linking study participant identification number to each subject, and this will be stored separately from study data. Participants will be assured that all data they provide to the study will be confidential to this study, unless it is necessary to “alert” the patient and possibly also their physician because of a laboratory value outside of the normal ranges that reflects a risk requiring immediate medical attention. All reports will use aggregate data. Subject names or other identifiers will not be reported. All quotes shared collected from the interviews will be de-identified for privacy. No persons from the recruitment sites will handle or have access to personal health information or participant survey data.

Data will be stored in REDCap, a secure, web-based application hosted at the University of Michigan. Analyses will be conducted using Atlas.ti. This data will be used to conduct a final refinement of treatment content as needed.

To ensure the proper monitoring of the safety of all participants and the quality of data collected, a Data Safety and Monitoring Board (DSMB) will be established that will follow techniques suggested in the literature (Damocles, et al, 2005). The board will consist of Drs. [name], [name], and [name]. In addition, five outside members, who are not involved with the study, will serve on the DSMB **as voting members** and will be identified at a later date. Voting members will consist of University professors with experience and expertise in clinical diabetes intervention research to ensure consistency and quality of input.

## **6.0 GROUP LEADERS & TRAINING**

To ensure staff participation in data safety and monitoring activities, all members of the project team (research assistants and staff) will be trained on the specifics of the data safety and monitoring plan. Field staff will be trained on what constitutes an adverse event to a participant and instructed to report any adverse events immediately to the principal investigator, [name].

All questionnaires and instrumentations are standardized measures that have been used in our own trials and in other diabetes research and there are no significant risks anticipated related to the completion of them. However, breaks will be given as needed to reduce fatigue, or measures read to adolescents, and research assistants will be appropriately trained to obtain personal information in a sensitive fashion. Research staff will be trained in research ethics, confidentiality protection, and HIPAA prior to and throughout the study period. All CDCESs in this study are either a Registered Dietitian Nutritionist RDN) or Registered Nurse (RN) and are certified through the Certification Board for Diabetes Care and Education. The extensive CDCES certification process ensures health care professionals possess comprehensive knowledge and experience in prediabetes, diabetes prevention, and diabetes management. [name], RDN, CDCES has been working with people with diabetes for 6 years and a CDCES for 2 years. [name], RDN, CDCES has been working with people with diabetes for 28 years and a CDCES for 24 years.

The PI will monitor adverse events throughout the clinical trial period. To ensure staff participation in data safety and monitoring activities, all members of the project team (research assistants and staff) will be trained on the specifics of the data safety and monitoring plan. Field staff will be trained on what constitutes an adverse event to a participant and instructed to report any adverse events immediately to the principal investigator, [name].

## **7.0 MEASURES**

### **Primary Outcome Measures**

Metabolic Control will be measured via hemoglobin A1c (HbA1c). HbA1c will be collected using the DCA 2000 point-of-care testing instrument.

Depression will be measured using the PHQ-9 (score  $\geq 10$ ) and The BDI-II, a 21-item self-administered questionnaire used to assess symptoms of depression. Depression will be measured using the Beck Depression Inventory (BDI-II). BDI-II items have been designed to correspond with DSM-IVTR diagnostic criteria. The BDI-II has been shown to have excellent test-retest reliability and validity when used in general populations as well for use with diabetes samples.

Regimen adherence will be measured using the Perceived Diabetes Self-Management Scale, a self-report questionnaire used to measure a broad range of management behaviors, such as insulin management, dietary management, blood glucose monitoring, symptom response, and parent assistance/supervision.

### **Secondary Outcome Measures**

BMI will be calculated using height and weight. Height will be measured using a stadiometer. Weight will be measured on a high quality, calibrated digital scale. BP will be measured using the auscultatory method.

Diabetes Social Support will be measured using the Diabetes Social Support Questionnaire. Diabetes-related Distress will be measured using Diabetes Distress Scale (SF-12) and lastly, a validated Diabetes Quality of Life will be used to measure quality of life. Participants will also complete questionnaires that assess socio-demographic, behavioral, psychosocial, and health services utilization and are

validated in diverse populations with diabetes.

**Specific Aim 1:** Qualitative analyses will be conducted during the development phase and on the post-intervention focus groups and interviews. First, we will develop codes utilizing a grounded theory approach and will start with the formulation of categories and definitions developed directly from the text. Content from transcripts will be coded for themes and patterns. Through this process a coding manual and definitions will be finalized. The refined manual will be used to guide ongoing coding and pairs of coders will read subsequent transcripts keeping codes that achieve 80% agreement on code application. Analyses will be conducted using Dedoose. This data will be used to conduct a final refinement of treatment content as needed.

**Specific Aim 2:** The proposed study includes a sample size of 60 Black men and women, 30 in the intervention arm and 30 in the control arm. We will assess the impact of the intervention on HbA1c (primary outcome) and diabetes management (secondary outcomes) using multilevel modeling, with intervention group as a between-subjects factor (2 levels) and time as a within subjects factor (3 levels). HbA1c, depression symptoms, diabetes self-management, and social support at baseline and 3 months will be used as the dependent variables. Independent variables include intervention group, time of assessment, and interaction between time and intervention group. Random effects will be allowed for the intercept (to allow differences in baseline measurements) and the slope (to allow differences in the trajectories of change). Covariates e.g. length of time since diabetes diagnosis, age will be tested as predictors of the outcome and retained if significant at  $p < .10$ .

**Power Analysis:** Assuming 20% attrition, we expect a final sample size of 48, approximately 12 per group (with 2 groups in the treatment arm). If we assume correlations of 0.25 between successive measurements of HbA1c, then this sample size will yield power of 0.8 to detect a difference of 0.6 standard deviation between average values of HbA1c in treatment and control groups.

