## **Online Diabetes Education Project: Virtual Diabetes Self-Management Education and Support Intervention IRB Protocol**

### **1.0 PHASE II RESEARCH PLAN (Pilot Randomized Control Trial, 3 months)**

During Phase II we will be conducting a 3 month pilot randomized controlled trial (RCT) of Virtual Diabetes-Self Management Education and Support (DSME/S), the treatment adapted in Phase I, to evaluate participant recruitment and retention rates, treatment and intervention satisfaction and estimate intervention effect sizes on our primary outcome of glycemic control (HbA1c) as well as on secondary outcomes such as diabetes-related distress, self-management behaviors and diabetes social support at baseline and treatment termination. Data will be collected at baseline and three months (treatment termination) at a federally qualified health center, telephonically, or virtually. Participants will be randomized to the virtual empowerment-based DSMES or a control group. All virtual DSME intervention group sessions will be held on an online platform, Zoom Med. The baseline assessment and intervention period will consist of 14 weeks. In the first 2 weeks participants will complete baseline questionnaires, interviews, and physiologic testing at a federally qualified health center, telephonically, or virtually. In weeks 3 to 10, participants will be simultaneously enrolled in 8 weekly virtual DSME classes. In weeks 13 and 14 of the intervention, participants will complete the post-treatment assessment battery (See Table 1). Patients who do not complete the intervention phase will also be invited to participate in the treatment termination assessment. The physiologic testing part of the assessment will be held at Detroit Community Health Connection, Inc. (DCHC) and other community-based locations TBD, based on participant feedback, telephonically, or virtually. DCHC is a non-profit community-based primary care organization that provides medical and dental services to the insured, uninsured and underinsured at six federally qualified health centers in the city of Detroit. Data analyses and dissemination of study findings are anticipated to be completed in months 11-12 of the study funding period. In Phase III of this project, we will be conducting qualitative interviews to better understand the acceptability and sustainability of the intervention as routine practice in a community-based clinic.

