**Table 1. Detailed timeline of Phase I and Phase II**

TIMELINE	Q1			Q2			Q3			Q4		
	Dec 20	Jan 21	Feb 21	Mar 21	Apr 21	Jun 21	Jul 21	Aug 21	Sep 21	Oct 21	Nov 21	Dec 21
Study Activities												
Phase I												
Focus Group Recruitment	■											
Hire & Train Research Staff	■											
Conduct Focus Groups		■										
Analyze Focus Group Data		■	■									
Adapt Intervention Materials			■	■	■							
Intervention Recruitment		■	■	■	■	■						
Phase II RCT												
Randomization			■	■	■	■						
T0 Baseline Assessment							■					
T1 Post-Intervention Assessment								■				
Phase III Data Analysis												
Interviews and Focus Groups (participants and practitioners)										■	■	
Analyze and disseminate data										■	■	

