Based on our previous work, the ***long-term goal*** of our research is to determine the most effective, practical, and sustainable approaches to provide virtual diabetes self-management education and support (DSME/S) to increase accessibility to DSME/S in clinical and non-clinical settings. The ***objective*** of this proposal is to examine the relative effectiveness, feasibility and acceptability of virtual DSME compared to a control group. To accomplish this objective, we will engage in a developmental phase and a validation phase [pilot randomized controlled trial (RCT)]. The RCT will be conducted with N=60 Black adult residents of Detroit, MI. Participants will be randomized to an enhanced usual care group or to the tailored virtual DSME/S. We ***hypothesize*** that 1) participants in the virtual diabetes approach will have improved outcomes over the control group, and 2) an evaluation of measures will confirm efficacy of the intervention. Measures will be collected at baseline and 3-months. The primary outcome will be change in A1c, depression, and self-management behaviors at baseline and post-intervention. Secondary outcomes include changes in weight, blood pressure, quality of life, and diabetes related distress. We ***hypothesize*** that 1) participants in virtual DSME/S approaches will have improved outcomes over the control group, and that 2) participants in the empowerment-based virtual DSME/S will achieve DSME/S skills at significantly higher levels than participants in the control group.

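### The HbA1c model assumes three time points when two are scheduled, its group-by-time effect is less precise than a baseline-adjusted one, and the stated 0.80 power belongs to neither

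*Combined protocol and SAP*

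**What the plan says.** The Specific Aim 2 analysis paragraph in section 7.0 (under Secondary Outcome Measures) sets up a multilevel model "with intervention group as a between-subjects factor (2 levels) and time as a within subjects factor (3 levels". The next sentence names only two occasions: "HbA1c, depression symptoms, diabetes self-management, and social support at baseline and 3 months will be used as the dependent variables". The fixed effects are given as "Independent variables include intervention group, time of assessment, and interaction between time and intervention group", and the random part as "Random effects will be allowed for the intercept (to allow differences in baseline measurements) and the slope". No covariance structure is stated. HbA1c at baseline is therefore a response in the model, and it is not named as a covariate.

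The schedule has two assessments. Section 1.0 says "Data will be collected at baseline and three months (treatment termination", and section 2.0 says "Measures will be collected at baseline and 3-months". Specific Aim 3 in section 3.0 and the Follow-Ups paragraph in section 5.0 agree. Table 1 lists a baseline T0 and a "T1 Post-Intervention Assessment", whereas the Baseline Assessment paragraph in section 5.0 labels the final visit T2.

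The Power Analysis paragraph assumes 20% attrition (48 completers) and a correlation of 0.25 between successive HbA1c measurements. It states power of 0.80 for a 0.6 SD gap between the arms' averaged HbA1c. It gives no alpha, sidedness or number of measurements.

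**The concern.** Sections 1.0 and 3.0 make an HbA1c effect size one of the pilot's products, to inform a larger trial. For that the estimand, the model and the stated precision must describe the same thing, and here they do not.

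- The model has one more time level than there are visits, and its random part may not be estimable from two visits.
- The plan does not say which coefficient is the treatment effect. The hypothesis in section 2.0 is only that "participants in the virtual diabetes approach will have improved outcomes over the control group". With two visits the usual choice is the interaction, which leaves precision unused.
- The 0.80 is quoted for a different quantity, so a reader cannot tell what the analysis can detect or how wide its interval will be.

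**Working it through.** **Inputs from the documents.** 60 randomised 1:1; 20% attrition, so 48 completers, taken as 24 per arm; r = 0.25; difference 0.6 SD.

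**Assumptions.** Alpha 0.05, two-sided, with one-sided also shown; the same HbA1c SD at both visits, scaled to 1; no clustering by session group. Power is from the noncentral t distribution.

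**Step 1: the plan's 0.80.** For an average of k equally correlated measurements, the variance of the arm difference is 2[1 + (k−1)r]/(24k).

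- k = 2: 2 × 1.25/48 = 0.0521, SE 0.228. Power 0.73 two-sided, 0.83 one-sided.
- k = 3: 2 × 1.5/72 = 0.0417, SE 0.204. Power 0.82 two-sided.
- 3-month means alone: 2/24 = 0.0833, SE 0.289. Power 0.53 two-sided, 0.66 one-sided.

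The nearest match is an average of three measurements, a design the protocol does not have. If a two-visit average includes baseline, where randomised arms have equal expectation, then 0.6 SD in the average requires 1.2 SD at 3 months. If the 3-month effect is 0.6 SD, the average differs by only 0.3 SD, and power is 0.25 two-sided, 0.36 one-sided.

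**Step 2: the two-visit contrasts at r = 0.25.**

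- Group by time (difference in change): 4(1−r)/24 = 4 × 0.75/24 = 0.1250, SE 0.354.
- Same contrast, keeping the 6 baseline-only dropouts per arm: 2[(1−r²)/24 + (1−r)²/30] = 2[0.9375/24 + 0.5625/30] = 0.1156, SE 0.340.
- Baseline-adjusted (ANCOVA or common baseline mean): 2(1−r²)/24 = 2 × 0.9375/24 = 0.0781, SE 0.280.

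| Contrast | Variance ratio | 95% CI half-width (SD) | Power for 0.6 SD, two-sided | One-sided |
|---|---|---|---|---|
| Group by time, completers | 1.60 | 0.71 | 0.38 | 0.51 |
| Group by time, with dropouts' baselines | 1.48 | 0.68 | 0.41 | 0.54 |
| Baseline-adjusted | 1 | 0.56 | 0.56 | 0.68 |

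Completers per arm needed for 0.80 power: 67 for group by time and 42 for baseline-adjusted, two-sided; 53 and 33 one-sided. The plan expects 24.

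**Step 3: other correlations.** With equal SDs the completers' variance ratio is 4(1−r)/[2(1−r²)] = 2/(1+r), which exceeds 1 for every r below 1. It is 1.33 at r = 0.5, 1.18 at 0.7 and 1.11 at 0.8. At r = 0.7 the half-widths are 0.45 and 0.42 SD, and two-sided power is 0.75 and 0.81. At 24 per arm, two-sided power of 0.80 needs r of about 0.74 for group by time and 0.69 for the adjusted comparison.

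**Step 4: simulation check.** In 100,000 simulated trials at r = 0.25, power was 0.383 for change and 0.548 for ANCOVA, the variance ratio was 1.55, and the half-widths were 0.71 and 0.57 SD. The small differences from the formulas reflect estimating the baseline slope.

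**Step 5: the random slope.** Code time as 0 and 1. Two visits supply three covariance elements: a + e, a + c, and a + 2c + s + e, where a is the intercept variance, s the slope variance, c their covariance and e the residual variance. That is four unknowns for three elements (rank 3 of 4), so s and e cannot be separated. With c fixed at zero the model is just identified, but the plan does not say this. Neither version changes the group-by-time estimate or its SE.

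**The case against.** The strongest reply is that little is broken. The sentence after the three-level statement names two occasions, so an analyst would fit two levels. The random slope does not alter the group-by-time estimate or its SE. The difference in change is a valid effect estimate, so baseline adjustment is an efficiency gain and not the repair of a bias. All of that is accepted.

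The size of the gain also depends on assumptions. It is large at r = 0.25 and modest at 0.7 or above. It presumes equal SDs: with a 3-month SD 1.2 times baseline the variance ratio is 1.36 at r = 0.25 and 1.03 at r = 0.7; with 0.8 times it is 2.07 and 1.59. The direction holds in all four cases, and 0.25 is the plan's own value.

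The documents do not show how 0.80 was obtained, and an average could simply mean an arm mean. On that reading, though, 3-month means give only 0.53 two-sided or 0.66 one-sided. None of the two-visit contrasts tried at 24 per arm and r = 0.25 reproduces 0.80; the closest is the one-sided two-visit average at 0.83.

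ANCOVA drops participants with no baseline HbA1c, which could happen where assessments are by telephone or virtual; a common-baseline model covers them. Finally, this is a pilot, so power is secondary. Precision of the effect size is not, and the plan makes a formal power claim.

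**Conclusion.** The concern holds and should be fixed. The number of time levels and the visit labels contradict the schedule, and the random-effects structure is not identified from two visits unless a constraint is added. The stated 0.80 does not describe the two-visit group-by-time contrast, whose power on the plan's own inputs is 0.38 two-sided or 0.51 one-sided.

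The baseline-adjusted comparison uses the same data and narrows the expected half-width by about a fifth at r = 0.25 (0.71 to 0.56 SD), less at higher correlations. It does not bring power back to 0.80 at r = 0.25.

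The power figures rest on an assumed alpha of 0.05. All figures assume equal SDs and no clustering. The Power Analysis paragraph places the treatment arm in two groups of about 12, and positive clustering would lower every power figure. With an assumed intraclass correlation of 0.01 to 0.05 in that arm only, the design effect there is 1 + 11 × ICC, and the adjusted half-width becomes 0.58 to 0.64 SD.

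**What to change.** - State two time levels, baseline and 3 months, and use one label for the second visit in Table 1 and section 5.0. If a third assessment was intended, reconcile the schedule with the model.
- Drop the random slope and specify an unstructured 2×2 covariance for the two visits.
- Name the treatment effect as the difference between arms in HbA1c at 3 months, preferably from a longitudinal model with a common baseline mean, which keeps participants missing one measurement. ANCOVA on baseline HbA1c is the alternative, with a stated rule for missing baselines.
- Restate the power for that contrast with alpha and sidedness, or replace it with the expected 95% CI half-width: about 0.56 SD (0.57 by simulation) at r = 0.25 with 24 per arm, before any allowance for session-group clustering. Say plainly that 0.6 SD is not detectable with 0.80 power at r = 0.25.

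The cost is a few sentences in section 7.0, the visit labels, and one degree of freedom. No further participants, visits or measurements are needed.

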**Specific Aim 3: Assess the impact intervention strategies developed in Aim 1 by:**

- conducting a pilot study of our DSME/S to evaluate participant recruitment and retention rates, treatment and intervention satisfaction and estimate intervention effect sizes on our primary outcome of glycemic control (HbA1c) as well as on secondary outcomes such as self-management behaviors, depression and diabetes social support at baseline and 3 months. Data from the pilot trial will help refine recruitment strategies, training materials, and protocol to be used in a larger clinical trial.
- conducting qualitative interviews to better understand the acceptability and sustainability of the intervention as routine practice in a community-based clinic.

**Overall Impact:** Data from the pilot RCT will help refine recruitment strategies, training materials, and the study protocol to be used in a larger cluster RCT. Our study will also identify strategies to increase patient participation in intervention research and improve dropout rates. This goal is in line with the mission of NIDDK to disseminate science-based information on diabetes, to improve people's health and quality of life.

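### Does choosing covariates by p < .10 from an open list undermine the HbA1c treatment estimate?

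*Combined protocol and SAP*

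**What the plan says.** The Specific Aim 2 paragraph of section 7.0 (Measures) gives one multilevel model: "Independent variables include intervention group, time of assessment, and interaction between time and intervention group". It applies to four outcomes: "HbA1c, depression symptoms, diabetes self-management, and social support at baseline and 3 months will be used as the dependent variables". The adjustment rule is "Covariates e.g. length of time since diabetes diagnosis, age will be tested as predictors of the outcome and retained if significant at" p < .10.

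That sentence names two covariates, diabetes duration and age, and leaves the list open. It does not say whether candidates are screened together or singly, whether arm is in the screening model, or whether the four outcomes share one set. No unadjusted analysis is named as the main one. The same section adds that "Participants will also complete questionnaires that assess socio-demographic, behavioral, psychosocial, and health services utilization", but does not call these covariates.

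On the treatment contrast, section 2.0 says "The primary outcome will be change in A1c, depression, and self-management behaviors at baseline and post-intervention", which points to group by time. The Power Analysis claims "power of 0.8 to detect a difference of 0.6 standard deviation between average values of HbA1c in treatment and control groups", which can be read as a between-group comparison of levels.

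**The concern.** Data-driven covariate selection is usually discouraged in a randomised trial. The reported standard error ignores the selection step, the estimate depends on which covariates happen to pass a test, and an open list leaves room for choice after the data are seen. The questionnaires could supply many candidates. Because no unadjusted analysis is named, the rule acts on the only efficacy model in the plan. Specific Aim 3 wants HbA1c effect sizes to inform a larger trial, and section 2.0 states comparative hypotheses. An inflated error rate or an unstable estimate would harm both uses.

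**Working it through.** **Inputs.** From section 7.0 and the Power Analysis: 30 per arm at baseline; 20% attrition, so 60 × 0.8 = 48, or 24 per arm at 3 months; correlation r = 0.25 between measurements. Assumed: two-sided 5% level, dropout at random, 2 to 15 candidates. The simulations use a random intercept and two visits. The plan states a random slope and three time levels, but only two assessments are scheduled, and with two a slope variance cannot be separated from residual variance.

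**1. The plan's own figure.** Power 0.8 for 0.6 SD is approached by a baseline-adjusted mean of two follow-ups. The variance factor is (1 + r)/2 − r² = 0.625 − 0.0625 = 0.5625, SE = √(0.5625 × 2/24) = 0.217, 0.6/0.217 − 1.96 = 0.81, power 0.79. With the two planned visits the factor is 1 − r² = 0.9375, SE = 0.280, power 0.57. That is a separate matter; the covariate rule does not enter either calculation.

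**2. Why group by time is protected.** Write Y_it = a + b·g_i + c·t + d·g_i·t + β·x_i + u_i + e_it. The change between visits is c + d·g_i + (e_i1 − e_i0), so x_i drops out. With complete pairs the estimate of d is the difference in mean change whatever covariates are kept. A fitted example gave −0.41994 and SE 0.355 both with and without the covariate. Only participants with a baseline value alone let the covariate in.

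**3. How often covariates are kept.** With two covariates, a useless one is kept about 10% of the time. One correlated 0.20–0.30 with HbA1c (assumed) is kept 60–93% of the time, or 51–84% if the within-person correlation is 0.7. So the form of the model does depend on the data.

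**4. Type I error, nominal 5%.** Useless covariates screened jointly, 20,000 trials per row (simulation error about 0.15–0.18 points):

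| Candidates | Group × time, selected | Group × time, unadjusted | Average of visits, selected | 3-month, selected |
|---|---|---|---|---|
| 2 | 4.9% | 4.9% | 5.3% | 5.2% |
| 6 | 5.1% | 5.1% | 5.7% | 5.3% |
| 10 | 5.2% | 5.1% | 6.4% | 6.0% |
| 15 | 5.2% | 5.1% | 7.2% | 6.5% |

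- Keeping two covariates regardless of p gave 4.8–5.2% for the two between-group contrasts.
- Screening singly without arm gave 5.0% (average) and 4.8% (3-month) with 2 candidates, and 5.4% and 4.8% with 15. Screening singly with arm gave 6.9% and 6.0% with 15.
- Further runs of 4,000 trials analysed the 3-month score or the change score in 48 people. Two candidates gave 4.3–5.7% (unadjusted 4.4–5.2%). Ten gave 5.0–5.2% screened without treatment and 6.2–6.6% with it. Fifteen screened with treatment gave 7.6–8.2% (unadjusted about 5.5%).

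**5. Movement of the estimate.** With two useless covariates, the selected estimate differs from the fixed-set estimate by an SD of 0.012 outcome SD (group × time) or 0.033 (3-month). Against the 0.6 SD target, 0.012/0.6 = 2% and 0.033/0.6 = 5.5%. These are standard deviations, not limits: 5% of trials moved by more than 0.024 (4% of the target) and 0.07 (about 12%) respectively.

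**6. What a fixed pair would buy.** Relative to no adjustment, the spread of the group × time estimate changes by +0.1% if both covariates are useless and by −0.4% if each correlates 0.25 with HbA1c. For the average contrast the changes are about +2% and −8%; for the 3-month contrast, +1.0 to +1.5% and about −5%.

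**7. Naming group × time is not free.** With 30 and 24 per arm and r = 0.25, the variance per arm of the 3-month mean is 0.9375/24 + 0.0625/30 = 0.0411. That of the baseline mean is 1/30 = 0.0333, and their covariance is 0.25/30 = 0.0083. The SE is √[2(0.0411 + 0.0333 − 0.0167)] = 0.34 for group × time and √(2 × 0.0411) = 0.29 for the 3-month contrast.

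**The case for a change.** The strongest case for a change is that the list is open, so no simulation bounds the effect. Fifteen candidates screened with treatment in the model reach about 8%. An analyst who reported the best p-value among candidate models would reach 5.6–8.2% with 2 candidates and 11–12.5% with 15. Even group by time is not wholly immune: one run of 8,000 trials with 15 candidates gave 5.5% against 4.8% unadjusted. The rule does not restrict covariates to baseline values, although the surveys are repeated at 3 months. Closing the list costs a sentence or two.

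The pre-specification point stands: the wording is loose, and a named list would be better practice. The size argument stands only in part. No section gives 6, 10 or 15 candidates; two are named, and both are settled before treatment starts. Choosing the best treatment p-value is not the stated rule, which tests covariates against the outcome. Screening without arm, an equally natural reading, shows no inflation. The 8.2% figure comes from regressing the change score on candidates, which is not the planned main-effect adjustment. The average of two visits includes a pre-treatment measurement, so it is a weak reading of a treatment effect.

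**Conclusion.** The plan leaves out a detail, and no change is needed. For group by time, the contrast that sections 2.0 and 7.0 point to, fixing the covariates would leave type I error at about 5% and alter precision by between +0.1% and −0.4%. For between-group contrasts with the two named covariates, the excess is about 0 to 0.3 points in the larger runs and about half a point in the smaller ones. Inflation to roughly 6–8% depends on an assumed list of 10 to 15 candidates, with treatment in the screening model, and mostly on a between-group contrast.

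An analyst can sensibly fill the gap by writing down a short list of baseline covariates before fitting the model and showing the unadjusted result beside the adjusted one. Replacement text that also fixed group by time as the treatment estimate would commit the trial to an SE of about 0.34 SD where the 3-month contrast has 0.29, which is a choice with a cost. These conclusions assume dropout at random, a within-person correlation of 0.25, two visits and a random intercept. The stated three time levels, the random slope and the power figure are separate questions that this conclusion does not settle.
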